6.9.2.1 Duplicate Values on the Same Day

If more than one value is reported on the same day, then the result based on the following convention will be used for analysis visit window programming. This needs to be done before creating any analysis visits or time points including baseline or screening.

Variable Type	Assessment	Convention
Continuous variable	Imaging	Last value on that day based on non-missing time. If time is missing for all values on the same day, then the value corresponding to the scheduled visit will be used.
	PTA Assessments	
	Tympanometry	
Categorical variable	Imaging	For complete closure of TMP, Last value on that day based on non-missing time. If time is missing for all values on the same day, then the value corresponding to the scheduled visit will be used.

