- h. For multiple dose expansion, ASP0598 Otic Solution or placebo administration on Day 15 and Day 29 will be conducted in the case that the TMP closure is not confirmed. If the treatment is not conducted on these visits, imaging pictures and Microscopic ear examination for skin local reaction after the drug administration will be skipped.

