AE: adverse event; CBC: complete blood count; EOS: end of study; SAD: single ascending dose; TM: tympanic membrane

- a. Vital Signs include blood pressure, body temperature, and heart rate.
- b. Includes all medications taken within 28 days prior to ASP0598 Otic Solution or placebo administration at Day 1.
- c. AEs will be collected from the time of informed consent through Day 57 or EOS. Any AEs ongoing at Day 57 or EOS Visit must be followed until resolution or investigator determines the event to be stable. AEs should be assessed at least monthly.
- d. ASP0598 Otic Solution or placebo will be applied onto the remaining tympanic membrane under a microscope with a 22-gauge blunt needle. After ASP0598 Otic Solution or placebo administration, subjects will be required to remain on their side with the treated ear facing up for at least 15 minutes. Please see the Pharmacy Manual, Section 9.4: Dose Administration for detailed instructions.
- e. Otology examinations will be performed for both ears at the screening visit.
- f. Microscopic Ear examination will be performed prior to and 60 (± 5) minutes after ASP0598 Otic Solution/placebo administration. Skin local reaction at the application site will be evaluated by Modified Brighton Grading Scheme (Appendix 12.9) at 60 (± 5) minutes after ASP0598 Otic Solution/placebo administration.
- g. Ear cleaning will not be conducted between Days 2 – 29, unless it is absolutely necessary. Investigators will not clean the treated ear by suctioning unless subject's experience uncomfortable ear discharge.
- h. At Day 1, imaging pictures will be taken at the following time points: pre-dose, immediately after, 30 (± 5) minutes, and 60 (± 5) minutes after the ASP0598 Otic Solution or placebo administration.
- i. At Day 57 or EOS, the whole TM should be visible before taking imaging picture. If the whole TM is not visible, the investigator should clean the ear canal.
- j. Bone conduction testing at Day 2, 8, 15, 29 will be tested only at 1, 2 and 4 kHz (ototoxicity assessment).
- k. Urine or serum pregnancy test will be performed in women of childbearing potential.
- l. Day 1, PK blood draw will be performed at the following time points: pre-dose (-15) minutes, 30 (± 5) minutes and 60 (± 5) minutes after ASP0598 Otic Solution or placebo administration into the affected ear.

Table 3 Schedule of Assessments – Single Dose Expansion

| | Screening | Randomization | Observation | | | Day 85 Last Visit/ EOS |

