- c. AEs will be collected from the time of informed consent through Day 85 or EOS. Any AEs ongoing at Day 85 or EOS Visit must be followed until resolution or investigator determines the event to be stable. AEs should be assessed at least monthly.
- d. ASP0598 Otic Solution or placebo will be applied onto the remaining tympanic membrane under a microscope with a 22-gauge blunt needle. After ASP0598 Otic Solution or placebo administration, subjects will be required to remain on their side with the treated ear facing up for at least 15 minutes. Please see the Pharmacy Manual, Section 9.4: Dose Administration for detailed instructions.
- e. Otology examinations will be performed for both ears at the screening visit.
- f. Days 1, 15 and 29, microscopic ear examination will be performed prior to and 60 (± 5) minutes after ASP0598 Otic Solution/placebo administration. Skin local reaction at the application site will be evaluated by Modified Brighton Grading Scheme (Appendix 12.9) at 60 (± 5) minutes after ASP0598 Otic Solution/placebo administration.
- g. Ear cleaning will not be conducted between Days 2 – 57, unless it is absolutely necessary. Investigators will not clean the treated ear by suctioning unless subjects experience uncomfortable ear discharge).
- h. At Days 1, 15, and 29, imaging pictures will be taken at the following time points: pre-dose, immediately after, 30 (± 5) minutes, and 60 (± 5) minutes after the ASP0598 Otic Solution or placebo administration.
- i. At Day 85 and/or EOS, the whole TM should be visible before taking imaging picture. If the whole TM is not visible, the investigator should clean the ear canal.
- j. Bone conduction testing at Day 8, 15, 22, 29, 36 and 57 will be tested only at 1, 2 and 4 kHz (ototoxicity assessment).
- k. Urine or serum pregnancy test will be performed in women of childbearing potential.
- l. Day 1 and Day 29, PK blood draw will be performed at the following time points: pre-dose (-15) minutes, 30 (± 5) minutes and 60 (± 5) minutes after ASP0598 Otic Solution or placebo administration into the affected ear.

Table 5 Schedule of Assessments – Multiple Dose Expansion

| | Day | Screening | Randomization | Observation | | | | | |
|---|------|--------------------|----------------|------------------|------------------|----------------|----------------|----------------|-------------------------------|
| | | Day – 28 to Day -1 | Day 1 | Day 15 | Day 29 | Day 43 | Day 57 | Day 85 | Day 113 Last Visit/ EOS |

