- d. ASP0598 Otic Solution or placebo will be applied onto the remaining tympanic membrane under a microscope with a 22-gauge blunt needle. After ASP0598 Otic Solution or placebo administration, subjects will be required to remain on their side with the treated ear facing up for at least 15 minutes. Please see the Pharmacy Manual, Section 9.4: Dose Administration for detailed instructions.
- e. Otology examinations will be performed for both ears at the screening visit.
- f. Microscopic Ear examination will be performed prior to and 60 (± 5) minutes after ASP0598 Otic Solution/placebo administration. Skin local reaction at the application site will be evaluated by Modified Brighton Grading Scheme (Appendix 12.9) at 60 (± 5) minutes after ASP0598 Otic Solution/placebo administration.
- g. Ear cleaning will not be conducted between Days 2 – 85, unless it is absolutely necessary. Investigators will not clean the treated ear by suctioning unless subjects experience uncomfortable ear discharge).
- h. At Days 1, 15, and 29, imaging pictures will be taken at the following time points: pre-dose, immediately after, 30 (± 5) minutes, and 60 (± 5) minutes after the ASP0598 Otic Solution or placebo administration.
- i. At Day 85 (SAD) or Day 113 (single dose expansion) and/or EOS, the whole TM should be visible before taking imaging picture. If the whole TM is not visible, the investigator should clean the ear canal.
- j. Bone conduction testing at Day 15, 29, 43, 57, and 85 will be tested only at 1, 2 and 4 kHz (ototoxicity assessment).
- k. Urine or serum pregnancy test will be performed in women of childbearing potential.
- l. ASP0598 Otic Solution or placebo administration on Day 15 and Day 29 will be conducted in the case that the TMP closure is not confirmed.

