6.6 Dose Modification

SAD and single dose expansion

Not Applicable.

MAD

On Day 15 or Day 29, treatment can be skipped at the Investigator's discretion based on safety reasons that interrupt IP administration (e.g., ear canal skin irritation, mild otorrhea). Subjects should be encouraged to return to the office for evaluation and additional IP administration within the Day 15 or Day 29 visit windows. In the case that the investigator is unable to conduct IP administration for anything other than safety reasons, consultation with the sponsor may be required.

Multiple dose expansion

The statement above for MAD is also applicable to the multiple dose expansion. Additionally, the treatment on Day 15 or Day 29, treatment will be skipped in cases where complete closure is confirmed. If the perforation is detected on Day 29 after treatment was skipped on Day 15, IP administration can be conducted.

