6.9.2.2 Analysis Visit Windows

Table 6 Analysis Visit Windows: Imaging

Analysis Visit	Target Study Day	Analysis Visit Window (Study Day)			
		SAD	Single dose expansion	MAD	Multiple dose expansion
Baseline ^a	1	≤ 1	≤ 1	≤ 1	≤ 1
Day 2 ^b	2	2	NA	NA	NA
Day 2 ^c	2	2 to 3	NA	NA	NA
Day 3 ^d	3	3 to 4	NA	NA	NA
Week 1	8	5 to 11	NA	2 to 11	NA
Week 2	15	12 to 18	2 to 18	12 to 18	2 to 22
Week 3	22	NA	NA	19 to 25	NA
Week 4	29	19 to 39	19 to 39	26 to 32	23 to 36
Week 5	36	NA	NA	33 to 39	NA
Week 6	43	NA	NA	NA	37 to 50
Week 8	57	≥ 40	40 to 74	40 to 74	51 to 71
Week 12	85	NA	≥ 75	≥ 75	72 to 99
Week 16	113	NA	NA	NA	≥ 100
EOS ^e		≥ 2	≥ 2	≥ 2	≥ 2

For the results corresponding to post-dose timepoints immediately after, 0.5 hour and 1 hour post-dose on the dosing days, analysis timepoint will be assigned same as the nominal timepoint and these results will not be used to identify the value for analysis.

^a Baseline value for the above data is based on the last available non-missing value on or prior to the first dose day (Day 1) of study drug within the visit window.

^b For cohorts 1, 2 and 3.

^c For cohorts 4, 5 and 6.

^d Day 3 evaluations will only be performed for cohorts 1, 2 and 3.

^e EOS value for the above data is based on the last available non-missing post-baseline value within the visit window.

Table 7 Analysis Visit Windows: PTA Assessments, Tympanometry and Tympanogram

Analysis Visit	Target Study Day	Analysis Visit Window (Study Day)			
		SAD	Single dose expansion	MAD	Multiple dose expansion
Baseline ^a	1	≤ 1	≤ 1	≤ 1	≤ 1
Week 8	57	≥ 40	NA	NA	NA
Week 12	85	NA	≥ 75	≥ 75	72 to 99
Week 16	113	NA	NA	NA	≥ 100
EOS ^b		≥ 2	≥ 2	≥ 2	≥ 2

^a Baseline value for the above data is based on the last available non-missing value on or prior to the first dose day (Day 1) of study drug within the visit window.

^b EOS value for the above data is based on the last available non-missing post-baseline value within the visit window.

To identify the value for the analysis, the following rules will apply excluding baseline and EOS:

1. For an analysis visit, if a subject has more than one result included within a window, the value closest to the target study day will be used. In case of ties between values located on different sides of the target study day, the later assessment will be used.

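### SAP 6.9.2.1 keeps each day's last image before Table 6 bars post-dose images, so in the written order no dosing-day image survives

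*SAP*

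**What the plan says.** SAP 6.9.2.1 applies whenever a subject has more than one imaging value on a day. TMP size and closure follow the same convention, worded for closure as "For complete closure of TMP, Last value on that day based on non-missing time". If no clock times exist, the scheduled-visit value is used. On sequence the section says "This needs to be done before creating any analysis visits or time points including baseline or screening". It makes no exception for pre-dose or post-dose images.

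The note to Table 6 in SAP 6.9.2.2 gives images taken immediately, 0.5 h and 1 h after a dose their nominal time point and adds that "these results will not be used to identify the value for analysis". Footnote a of that table takes baseline as the last non-missing value up to and including Day 1. Protocol Section 9 instead ties baseline to the administration of study drug.

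The image schedule is in Protocol 1.3. For SAD and single dose expansion: "At Day 1, imaging pictures will be taken at the following time points: pre-dose, immediately after", then 30 and 60 minutes. For MAD and multiple dose expansion: "At Days 1, 15, and 29, imaging pictures will be taken at the following time points: pre-dose, immediately after", again with 30 and 60 minutes. Protocol 7.1.1 sends every image for central measurement.

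In multiple dose expansion, dosing on Days 15 and 29 "will be conducted in the case that the TMP closure is not confirmed" (Table 5, footnote l). Figure 7, footnote h, covers an undosed visit: "If the treatment is not conducted on these visits, imaging pictures and Microscopic ear examination for skin local reaction after the drug administration" are then omitted. Protocol 6.6 also allows a dose to be skipped at the investigator's "discretion based on safety reasons that interrupt IP administration".

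**The concern.** Taken in the stated sequence, the two rules cancel each other on every dosing day. The same-day rule keeps the 60-minute image and the Table 6 note then disqualifies it.

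**Baseline.** Baseline TMP size and ratio feed change from baseline, the MMRM covariate and the size group in the Mantel-Haenszel (MH) test. SAP 6.4.2 defines that group from baseline central imaging. SAP 6.4 lists it separately from the stratification factor, which Protocol 6.3.6 takes from Screening images. Under the fallback both rest on the Screening image and the Day 1 pre-dose image goes unused.

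**Weeks 2 and 4 in multiple dose expansion.** Whether a value survives depends on whether the ear was dosed, and so mainly on whether it had closed. SAP 6.1 computes percentages on non-missing subjects, so central-reader closure is inflated. SAP 6.4.3 puts these visits through the MMRM, reported with CIs and p-values. The MMRM assumes data missing at random, but here missingness depends on the lost value itself. The sensitivity analysis in SAP 6.9.3.5 would not repair this. It first fills intermittent gaps within each treatment group, drawing on the mostly closed ears that remain.

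**Working it through.** The plan gives no figure on this point to reproduce. The check has four steps.

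**1. Trace of the records.** Inputs: the scheduled images from Protocol 1.3 and the windows in SAP Table 6. Written order: last image per day, then the post-dose bar, then the windows. Reversed order: the bar first.

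| Part, days dosed | Written order: baseline | Written order: Weeks 2 and 4 | Reversed order |
|---|---|---|---|
| SAD, Day 1 | Screening | kept | Day 1 pre-dose; none missing |
| Single dose expansion, Day 1 | Screening | kept | Day 1 pre-dose; none missing |
| MAD, Days 1, 15, 29 | Screening | both missing | pre-dose images on Days 1, 15, 29; none missing |
| Multiple dose expansion, Days 1, 15, 29 | Screening | both missing | pre-dose images on Days 1, 15, 29; none missing |
| Multiple dose expansion, Days 1, 15 | Screening | Week 2 missing, Week 4 kept | none missing |
| Multiple dose expansion, Day 1 only | Screening | both kept | none missing |

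In the multiple dose parts, Day 15 and Day 29 are the only scheduled imaging days in the Week 2 and Week 4 windows, so no other scheduled visit fills the gap.

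**2. Counts.** Baseline: 20 + 39 + 16 + 39 = 114 planned subjects at most, with Screening running from Day -28. MAD: 7 post-baseline visits × 16 subjects = 112 values, of which 2 × 16 = 32 can be lost.

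**3. Week 2 closure in multiple dose expansion.** Let p be true closure at Day 15 and q the share of open ears left undosed. Neither is given in the documents, so both are assumed. With 13 subjects per arm:

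- values kept = 13[p + (1 − p)q]
- apparent closure = p / [p + (1 − p)q]

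| p | q = 0 | q = 0.10 |
|---|---|---|
| 0.05 | 0.7 kept, 100% | 1.9 kept, 34% |
| 0.10 | 1.3 kept, 100% | 2.5 kept, 53% |
| 0.40 | 5.2 kept, 100% | 6.0 kept, 87% |
| 0.80 | 10.4 kept, 100% | 10.7 kept, 98% |

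For p = q = 0.10: 13 × (0.10 + 0.09) = 2.5 and 0.10/0.19 = 53%.

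**4. MMRM on the ratio.** There were 600 simulated trials in each of five scenarios, with 13 per arm and Weeks 2, 4, 6, 8, 12 and 16. Week 16 closure was 80% versus 10%, as in the sample size section. Assumed: Day 15 closure 10–60% on active and 2–10% on placebo, q of 0–10%, baseline ratio mean 20 (SD 10), site and central closure agree, no dropout. The SAP's model terms were fitted by REML with its two fallback covariances. The unstructured form was not fitted: only about 4–10 Week 2 values remain over both arms for 3 mean and 6 covariance parameters.

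| Scenario | Week 2 difference, all data | Written order (spatial power / compound symmetry) | Overstatement, points | Trials with a Week 2 or 4 term not estimable |
|---|---|---|---|---|
| 1 | −6.4 | −9.8 / −12.1 | 3.4 / 5.7 | 52% |
| 2 | −7.4 | −11.0 / −12.2 | 3.6 / 4.8 | 22% |
| 3 | −3.8 | −8.2 / −9.8 | 4.4 / 6.0 | 22% |
| 4 | −2.7 | −7.0 / −8.8 | 4.3 / 6.1 | 44% |
| 5 | −10.0 | −11.6 / −13.0 | 1.6 / 3.0 | 19% |

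Week 4 was overstated by 0.7–5.2 points. The largest change in the Week 16 estimate was 0.000. A separately written simulation agreed in direction: Week 2 overstated by about 1.3–4.2 points, terms not estimable in 10–39% of trials, Week 16 unchanged.

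**The case against.** The strongest reply is about intent. The Table 6 note sets aside three post-dose results. If the day had already been cut to one record, two of those could not exist. Planned images at different nominal times are not naturally duplicates, and reading 6.9.2.1 as limited to true duplicates gives both rules effect. That is probably what the authors meant. But the section is triggered by any second value on a day, and its only sentence on order names baseline explicitly.

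A second reply is that the error would show itself. MAD Weeks 2 and 4 would be largely empty at the interim analysis that precedes multiple dose expansion. That is a fair point for MAD. The baseline fallback is harder to see, because a value is still present.

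Third, the Screening image precedes treatment and is centrally read, and the protocol describes the condition as stable, so the fallback should not favour one arm. This stands: the baseline count measures exposure, and no bias from it has been shown. The departure from the protocol's baseline remains.

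Fourth, Weeks 2 and 4 are exploratory, MAD has no hypothesis tests, and multiple dose expansion may never open. The simulated sizes rest on assumed inputs and fallback covariances. The loss also requires recorded clock times. All of this stands and limits the impact.

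**Conclusion.** The concern holds. As written, SAP 6.9.2.1 followed by the Table 6 note removes every dosing-day image, and this follows from the text without any simulation.

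The impact is modest. Imaging baseline moves to Screening in all parts, and MAD loses up to 32 of 112 values. In multiple dose expansion, Week 2 and Week 4 central-reader closure and MMRM contrasts are distorted in a way that depends on outcome. The size of that distortion rests on assumed early closure rates and on how many open ears go undosed.

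Observed Week 12 and Week 16 closure is not affected. The Week 16 MMRM estimate did not move when there was no dropout. For subjects who discontinue early in multiple dose expansion, the last central-reader status before the event could also be lost; this was not sized. Investigator-assessed closure comes from the microscope examination and is outside the imaging rule. The point should be fixed before programming.

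**What to change.** Make this the first step of SAP 6.9.2.1: on dosing days, images with a nominal post-dose time point (immediately after, 0.5 h, 1 h) are excluded before the same-day convention is applied, so that the pre-dose image is the value for that day. Change the Table 6 baseline footnote to the last non-missing image before the first dose, in line with Protocol Section 9. Once the order is fixed the footnote change is largely redundant, but it removes the day-level wording. Table 7 and SAP 6.9.1.1 need no change.

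The cost is one sentence and one footnote. With this order the trace above gives the Day 1 pre-dose baseline in all four parts and no missing scheduled visit.

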6.9.2.2 Analysis Visit Windows

Table 6 Analysis Visit Windows: Imaging

Analysis Visit	Target Study Day	Analysis Visit Window (Study Day)			
		SAD	Single dose expansion	MAD	Multiple dose expansion
Baseline ^a	1	≤ 1	≤ 1	≤ 1	≤ 1
Day 2 ^b	2	2	NA	NA	NA
Day 2 ^c	2	2 to 3	NA	NA	NA
Day 3 ^d	3	3 to 4	NA	NA	NA
Week 1	8	5 to 11	NA	2 to 11	NA
Week 2	15	12 to 18	2 to 18	12 to 18	2 to 22
Week 3	22	NA	NA	19 to 25	NA
Week 4	29	19 to 39	19 to 39	26 to 32	23 to 36
Week 5	36	NA	NA	33 to 39	NA
Week 6	43	NA	NA	NA	37 to 50
Week 8	57	≥ 40	40 to 74	40 to 74	51 to 71
Week 12	85	NA	≥ 75	≥ 75	72 to 99
Week 16	113	NA	NA	NA	≥ 100
EOS ^e		≥ 2	≥ 2	≥ 2	≥ 2

For the results corresponding to post-dose timepoints immediately after, 0.5 hour and 1 hour post-dose on the dosing days, analysis timepoint will be assigned same as the nominal timepoint and these results will not be used to identify the value for analysis.

^a Baseline value for the above data is based on the last available non-missing value on or prior to the first dose day (Day 1) of study drug within the visit window.

^b For cohorts 1, 2 and 3.

^c For cohorts 4, 5 and 6.

^d Day 3 evaluations will only be performed for cohorts 1, 2 and 3.

^e EOS value for the above data is based on the last available non-missing post-baseline value within the visit window.

Table 7 Analysis Visit Windows: PTA Assessments, Tympanometry and Tympanogram

Analysis Visit	Target Study Day	Analysis Visit Window (Study Day)			
		SAD	Single dose expansion	MAD	Multiple dose expansion
Baseline ^a	1	≤ 1	≤ 1	≤ 1	≤ 1
Week 8	57	≥ 40	NA	NA	NA
Week 12	85	NA	≥ 75	≥ 75	72 to 99
Week 16	113	NA	NA	NA	≥ 100
EOS ^b		≥ 2	≥ 2	≥ 2	≥ 2

^a Baseline value for the above data is based on the last available non-missing value on or prior to the first dose day (Day 1) of study drug within the visit window.

^b EOS value for the above data is based on the last available non-missing post-baseline value within the visit window.

To identify the value for the analysis, the following rules will apply excluding baseline and EOS:

1. For an analysis visit, if a subject has more than one result included within a window, the value closest to the target study day will be used. In case of ties between values located on different sides of the target study day, the later assessment will be used.
2. For the categorical parameter, if a subject has more than one result included within a window, the assessment closest to the target study day will be used. In case of ties between results located on different sides of the target study day, the later assessment will be used.

6.9.3 Imputation Rules

6.9.3.1 Imputation of AE Onset Date

For AEs, a missing or incomplete onset date will be imputed according to the following conventions:

AE Onset Date Scenario	Convention
Completely missing or only the year is known	Non-missing first dose date of study drug
Only the month and year is known	Set surrogate onset date = AE onset date where day is set to the first day of that month and then apply the following rules: 1. If the month and year of the onset date is prior to the month and year of the first dose of study drug, then the surrogate onset date will be the imputed onset date. 2. If the month and year of the onset date is on or after the month and year of the first dose of study drug, then the imputed onset date will be the latest of the following non-missing dates: 
• First dose date of study drug• Surrogate onset date

If the above imputed onset date is after a complete AE end date, the imputed onset date will be the same as the complete AE end date.

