7.3.1 Time Period for Collecting Adverse Event and Serious Adverse Event Information

In order to identify any events that may be associated with study procedures and could lead to a change in the conduct of the study, Astellas collects AEs even if the subject has not received IP. AE collection begins after the signing of the ICF and will be collected until 14 days after the last study visit or when the subject is determined to be a screen failure.

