9.11 Additional Conventions

If the start and stop dates of AEs and concomitant medications are incomplete or onset date of TMP is incomplete, imputed dates will be used to determine whether an AE is/is not treatment emergent or to allocate a concomitant medication to the study period it was taken or to calculate time since TMP onset.

See the SAP for details of the definition for analysis windows to be used for analyses by visit.

Relevant listings will present the actual partial dates; imputed dates will not be shown.

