5 EFFICACY AND SAFETY ENDPOINTS

5.1 Primary Safety Endpoint(s)

- Treatment-emergent adverse events (TEAEs)
 - **TEAE:** an AE observed after starting administration of the study drug through end of study visit. If an AE occurs on Day 1 and the onset check box is marked “Onset after the dose of study drug” or the onset check box is left blank, then the AE will be considered TEAE. Refer to Section [6.9.1](#) for end day of end of study visit definition.
 - **Drug-related TEAE:** any TEAE with a causal relationship assessed as “yes” by the investigator. If the relationship is missing then it is considered as drug-related.

Imputed date for AE onset date may be used to determine TEAE (Section [6.9.3.1](#)).

The investigator will use the following definitions to rate the severity of each AE:

- Mild
- Moderate
- Severe

- Incidence of AEs of special interest will be defined as shown below.
 1. Cholesteatoma or neoplasm
 2. Ototoxic symptoms (tinnitus, sensorineural hearing loss, dizziness)
 3. Otitis media or otitis externa

AEs of special interest will be identified using custom MedDRA queries (CMQs). Detailed information about AEs of special interest is provided in Appendices 1, 2 and 3.

- Change from baseline in bone conduction hearing at 1, 2, 4 kHz by Pure Tone Audiometry (PTA)

A lower value indicates better level of hearing.

For the change from baseline, a negative value (decrease from baseline) indicates improvement (i.e., better level of hearing).

Mean bone conduction hearing (dB):

Arithmetic mean of the values at 1, 2 and 4 kHz. If the value is missing for any of the 3 frequencies, then the mean value will be set to missing.

- Change from baseline in Tinnitus Visual Analog Scale (TVAS)

The TVAS is a numeric scale and ranges from 0 (not at all strong or loud) to 10 (extremely strong or loud). A lower value indicates less level of discomfort.

For the change from baseline, a negative value (decrease from baseline) indicates improvement (i.e., less level of discomfort).

TVAS may be reported for one of the following areas: ear (left, right or bilateral) or other.

At a time point, if a subject did not experience tinnitus, TVAS will be reported as 0. In this case, the TVAS will be considered as 0 for all two areas.

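### An adverse event with only its onset year recorded is dated to the first dose even when that year precedes dosing, so a known pre-dose event can be counted as treatment-emergent unless a complete pre-dose end date or the Day 1 check box prevents it

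*SAP*

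**What the plan says.** SAP 6.9.3.1 handles incomplete AE onset dates in a two-row table.

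- First row: onset "Completely missing or only the year is known". The imputed value is "Non-missing first dose date of study drug".
- Second row: month and year known. The row compares them with the dosing date. "If the month and year of the onset date is prior to the month and year of the first dose of study drug", the first day of that month is used and the event stays before dosing. Otherwise the later of that day and the first dose date is used.
- Below the table, a sentence for both rows moves the onset back to a complete end date that precedes it. It begins: "If the above imputed onset date is after a complete AE end date, the imputed onset date will be the same as the complete AE".

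The imputed date feeds the classification of treatment emergence. Protocol 9.11 says "imputed dates will be used to determine whether an AE is/is not treatment emergent". SAP 5.1 is more permissive: "Imputed date for AE onset date may be used to determine TEAE". For an AE on Day 1, SAP 5.1 uses a check box. If it is marked as onset after dosing, "or the onset check box is left blank, then the AE will be considered TEAE".

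Pre-dose events are in the database, because under Protocol 7.3.1 "AE collection begins after the signing of the ICF".

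**The concern.** When the recorded year is earlier than the year of first dose, the event cannot have started after dosing. The year alone settles the matter, but the first row discards it. The same event recorded with its month as well would correctly stay before dosing, so classification depends on whether the month was entered and not on when the event began.

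The neighbouring rules keep a recorded year. For medication start dates (SAP 6.9.3.2) a missing month becomes January. For perforation onset (SAP 6.9.3.4) a year-only date becomes 30 June of that year.

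At stake is a false count in a primary safety endpoint, in groups of 4 (SAD active) or 6 (MAD active). Under Protocol 9.11 the listings show actual partial dates and not imputed ones. A reader could therefore see an onset year before dosing beside a TEAE flag.

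**Working it through.** The plan gives no figure to reproduce here, so the check applies the rules as written to test cases.

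**Inputs.** The date rules are from SAP 6.9.3.1 and the TEAE definition and check box from SAP 5.1. The limit of 28 days from consent to dosing is from Protocol 5.4.1. The first dose of 15 January 2022 is an assumed illustration.

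| Recorded onset | Recorded end | Onset under SAP | TEAE under SAP | Onset with year check | TEAE with year check |
|---|---|---|---|---|---|
| 2021 only | ongoing, partial or missing | 15 Jan 2022 | yes if box blank or after dose; no if before | 31 Dec 2021 | no |
| 2021 only | 20 Jan 2022 | 15 Jan 2022 | as above | 31 Dec 2021 | no |
| 2021 only | 10 Jan 2022 | 10 Jan 2022 | no | 31 Dec 2021 | no |
| 2021 only | 28 Dec 2021 | 28 Dec 2021 | no | 28 Dec 2021 | no |
| Dec 2021 | ongoing | 1 Dec 2021 | no | 1 Dec 2021 | no |
| 2022 only, or nothing | ongoing | 15 Jan 2022 | yes if box blank or after dose; no if before | 15 Jan 2022 | unchanged |

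Rows 1 and 5 show the defect. An ongoing event known to have begun in 2021 can be a TEAE if only the year is recorded, but not if December is recorded too. Rows 3 and 4 show the end-date sentence repairing the error.

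**Reach.** AEs are collected from consent, and consent precedes dosing by at most 28 days. A collected AE can have an onset in the previous year only if dosing falls on 1 to 28 January. That is 28 of 365 dates: 28/365 = 7.7%, assuming dosing is uniform over the year. At the maximum planned size of 20 + 39 + 16 + 39 = 114 subjects, 0.077 × 114 = 8.8, or about 9 subjects. This is a ceiling on subjects meeting the calendar condition, not a count of misclassified events.

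**Weight of one event.** If the subject has no other TEAE, one false TEAE adds 1/4 = 25 percentage points in a SAD active group and 1/6 = 17 points in a MAD active group.

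**Later-year onsets.** An onset known to be in the year after dosing is also moved to Day 1, where it cannot have begun. Such an event is post-dose on either date, so its TEAE status normally does not change. The exception is an onset after the SAP 6.9.1 cut-off: the end-of-study visit day or the planned final day, whichever is earlier, plus 7 days. Protocol 7.3.1 collects AEs for 14 days after the last visit. With a last visit on the planned day, this leaves 14 − 7 = 7 days in which such an onset could be collected and wrongly drawn into the count.

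**The case against.** The strongest reply is that the rule is a deliberate conservative default and the harmful case hardly arises. Much of this stands. Over-counting is consistent with SAP 5.1, where a blank check box makes a Day 1 event treatment-emergent and missing causality counts as drug-related. Under Protocol 10.2.2, conditions present at consent are medical history, so the event must start in the last weeks of December. The site would have to know its year but not its month. SAD and MAD sites enter Screening and Day 1 data within 24 hours (Protocol 10.1), which makes that unlikely. Safety analysis is descriptive, and the escalation stopping rules (Protocol 4.1.1.3) use specified events, relatedness and severity, not TEAE percentages.

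The default does not extend to this case, however. Dating an uncertain onset to first dose is cautious when the onset could be post-dose, and a known earlier year excludes that. The rule also applies to placebo, where a false TEAE would narrow a drug–placebo difference.

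A reader might infer two stronger points that the documents do not support.

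- That every year-only event from before dosing becomes a TEAE. The end-date sentence prevents this when a complete pre-dose end date exists. A check box recording onset before the dose would also exclude the event if it governs imputed Day 1 dates, which the SAP does not say.
- That later-year mis-dating distorts the safety results, because 113/365 = 31% of multiple dose expansion subjects have follow-up crossing a year end and an onset could be shifted by up to 112 days. The summaries in SAP 6.5.1 are counts and percentages and do not use onset day. Apart from the cut-off case, no planned TEAE count changes.

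**Conclusion.** The year-only rule is wrong as written, in a narrow case. Unless a complete pre-dose end date or a check box recording pre-dose onset overrides it, an event known to have begun in the year before dosing can be reported as treatment-emergent. This requires three things together: a first dose on 1 to 28 January, a year-only onset, and an event that is ongoing, ends on or after first dose, or lacks a complete end date. The 7.7% covers only the first condition and assumes uniform dosing dates. The documents give no frequency for the others, so the expected number of false TEAEs cannot be computed; it is very small. The bias is towards over-counting. The later-year defect matters only beyond the end-of-study plus 7 day cut-off. This is a minor point, worth correcting because the endpoint is primary and the rule overrides recorded data.

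**What to change.** Split the first row of the table in SAP 6.9.3.1:

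- Onset completely missing, or year equal to the first-dose year: first dose date, as now.
- Year before the first-dose year: 31 December of that year, hence not treatment-emergent.
- Year after the first-dose year: 1 January of that year.

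Keep the end-date sentence. In the test cases this makes every prior-year event non-treatment-emergent and leaves completely missing and same-year dates unchanged. A later-year event then drops out of the count only when the cut-off falls before 1 January; otherwise the year does not settle the matter and the event stays in.

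The cost is one table row and the matching program line, with no new data. Under SAP section 1 the change belongs before database lock and, for dose escalation, before the interim unblinding.
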